## General Statistical Methods and Types of Analyses

### Analysis Populations:

- Modified Intent-to-Treat Population – The modified intent-to-treat (mITT) population includes all randomized subjects with at least one post visit 2 study assessment. Efficacy analysis will be performed on the mITT population. Subjects in the mITT population will be analyzed as randomized.
- Per Protocol Population – The per protocol (PP) population includes subjects in the mITT population who do not have significant protocol deviations and who complete the study. Protocol deviations will be assessed prior to database lock and unmasking. Subjects in the PP population will be analyzed as treated.
- Safety Population – The safety population includes all subjects who have received at least one dose of the investigational product. Subjects in the Safety population will be analyzed as treated.

Summaries of the comfort data from the Comfort Assessment will be performed on the safety population from that Assessment. The statistical analysis of safety data will be performed for the safety population, separately for the Comfort Assessment and the Safety and Efficacy Assessment. The analysis of baseline and all efficacy data in the Safety and Efficacy Assessment will be performed for the mITT population. The efficacy analyses may also be performed on the PP population as sensitivity analyses.

### Sample Size:

The study is not powered to show statistical differences for any of the efficacy endpoints. The sample size was determined based on prior clinical trial experience in subjects with dry eye syndrome and is deemed to be sufficient to evaluate the safety and tolerability of TOP1630 Ophthalmic Solution in this population and to gather efficacy data that will aid in powering future clinical trials.

With a sample size of 60 subjects in the Safety and Efficacy Assessment, the study will have 79% probability of detecting AEs occurring at a rate of 5% or more in either treatment arm.

### Multiplicity Consideration:

There will be no adjustments for multiple endpoints or multiple treatment comparisons for this early phase, exploratory study.

### Safety Variables:

Adverse events will be coded using the MedDRA dictionary.

Frequencies and percentages of subjects with treatment-emergent adverse events (TEAEs), serious TEAEs, and TEAEs causing premature discontinuation will be provided by treatment group. An AE is treatment emergent if it occurs or worsens after the first dose of study treatment. Furthermore, frequencies will be given of subjects with TEAEs by system organ class and preferred term; by system organ class, preferred term and maximal severity; by system organ class and preferred term for treatment-related AEs; by system organ class, preferred term for SAEs; and by system organ class, preferred term, and time of onset. Separate summaries will be provided for ocular specific and all AEs (including systemic).

Other safety endpoints including visual acuity, slit-lamp biomicroscopy, corneal sensitivity, undilated fundoscopy, intraocular pressure (non-contact), and vital signs will be summarized by treatment group and visit using descriptive statistics. Changes or shifts from baseline will also be summarized where appropriate. For assessments performed by eye, study eye and fellow eye will be summarized separately. In addition, shifts from baseline to worst on-treatment value for ocular safety assessments will be summarized.

Safety summaries will be provided for the comfort and safety and efficacy portions of the study separately.

## LIST OF ABBREVIATIONS

AE	adverse event
ANCOVA	analysis of covariance
BCVA	best-corrected visual acuity
CAE®	controlled adverse environment
CFR	Code of Federal Regulations
CI	confidence interval
CRF	case report form
DES	Dry Eye Syndrome
DHHS	Department of Health and Human Services
eCRF	electronic case report form
EKG	Electrocardiograph
ERC	ethical review committee
ETDRS	Early Treatment of Diabetic Retinopathy Study
FDA	Food and Drug Administration
GCP	Good Clinical Practice
GMP	Good Manufacturing Practice
HIPAA	Health Information Portability and Accountability Act
ICF	informed consent form
ICH	International Conference on Harmonisation
IEC	Independent Ethics Committee
IND	investigational new drug application
IOP	intraocular pressure
IRB	institutional/independent review board
ITT	intent-to-treat
IUD	intra uterine device
IWRS	interactive web response system
KCS	keratoconjunctivitis sicca
Kg	Kilogram
LASIK	laser in situ keratomileusis
LOCF	last observation carried forward
logMAR	logarithm of the minimum angle of resolution
MedDRA	Medical Dictionary for Regulatory Activities
MGD	meibomian gland dysfunction
Mg	Milligram
mL	Milliliter
Mm	Millimeter
NEI	National Eye Institute
µg	microgram
µL	microliter
µm	Micrometer
mmHg	millimeters of mercury
OD	right eye

OPI	ocular protection index
OS	left eye
OSDI ®	ocular surface disease index
OU	both eyes
OTC	over-the-counter
PMNs	polymorphonuclear leucocytes
PP	per protocol
TID	three times a day (6 hour intervals in morning, afternoon, and evening)
SAE	serious adverse event
TFBUT/TBUT	tear film break-up time
TEAEs	treatment emergent adverse events
VA	visual acuity

## 1 INTRODUCTION

Dry eye syndrome (DES) is a common disorder affecting an estimated 25-30 million people in the United States, with prevalence estimates varying widely from 7.8% to almost 34%. Dry eye incidence rises sharply with age, and women are more affected than men, purportedly due to the pathophysiological role of androgens and the complex nexus of the endocrine-immunological systems. The Dry Eye Workshop (DEWS) has redefined dry eye as “a multifactorial disease of the tears and ocular surface that results in symptoms of discomfort, visual disturbance, and tear film instability with potential damage to the ocular surface, accompanied by increased osmolarity of the tear film and inflammation of the ocular surface”.

Approaches to treatment vary; however, disease modification usually has targeted the inflammatory aspects of the disease. The only currently approved therapies for dry eye are cyclosporine ophthalmic emulsion (Restasis®) and lifitigrast ophthalmic solution (Xiidra™). Despite a commonly reported side effect of burning/stinging while using these drops, Restasis® is widely prescribed and used for the treatment of DES. Xiidra™ has recently been approved and is also associated with burning and stinging following application. A well-tolerated drug that reduces the inflammatory response in DES would be a major step forward from current treatment options.

TopiVert’s narrow spectrum kinase inhibitors (NSKIs) promise to deliver long-term efficacy, improving both signs and symptoms of dry eye syndrome by effectively treating the underlying inflammation. Specifically, they target several important kinases (p38-alpha, syk and src family kinases src and lck) involved in the inflammatory cascade. TopiVert has demonstrated these kinases are up regulated in dry eye syndrome and inhibition leads to synergistic anti-inflammatory effects on key cell signaling pathways involved in inflammation. TOP1630 has been specifically designed to act locally at surface of the eye, with little or no systemic absorption, minimizing any untoward effects of the drug in the rest of the body. Thus TOP1630 has the potential to deliver a very favorable efficacy and safety profile for the sustained treatment of DES.

This study is the first in man for administration with TOP1630. Please refer to the Investigator’s Brochure for further information on TOP1630.

## 2 STUDY OBJECTIVES

In subjects with dry eye syndrome:

The primary objective of this study is to compare the safety and tolerability of TOP1630 Ophthalmic Solution to placebo.

The secondary objectives are to compare the efficacy of TOP1630 Ophthalmic Solution to placebo for the treatment of the signs and symptoms of dry eye syndrome.

### 3 CLINICAL HYPOTHESES

The clinical hypotheses for this study are that TOP1630 Ophthalmic Solution has an acceptable safety and toleration profile compared to placebo and demonstrates clinically meaningful differences on signs and symptoms in subjects with dry eye syndrome.

### 4 OVERALL STUDY DESIGN

This is a Phase 2, single-center, randomized, double-masked study designed to evaluate the safety, tolerability and efficacy of TOP1630 Ophthalmic Solution compared to placebo in subjects with dry eye syndrome.

For the Comfort Assessment, 8 subjects at least 18 years of age with a subject reported history of dry eye syndrome in both eyes and meeting all other study eligibility criteria will be randomized to receive 0.01% to 0.1% TOP1630 or placebo in a 3:1 ratio (6 subjects in the TOP1630 arm, 2 subjects in the placebo arm). The study will consist of two periods: the 1st period will consist of single or TID dosing over 24 hours (on up to three separate dosing occasions) with safety assessments during the subsequent 24 hours. The 2nd period will consist of TID dosing over days 8 to 11, followed by safety assessments over the subsequent 24 hours. The same subjects will proceed through both periods unless a study stopping criteria is met in which case a lower dose regime may be used for subsequent cohorts. A study flow chart appears below:

[figure not shown]
Visit 1a (Day 1): 0.01% or Placebo TID	Informed Consent Demographics, Medical/Medication & Ocular History Vital Signed Urine Pregnancy Testing (as needed) Visual Acuity, Baseline Slit Lamp Biomicroscopy, IOP and Comfort Assessment Morning 0.01% TOP1630 or Placebo Dose Slit Lamp Biomicroscopy, Comfort Assessment Afternoon 0.01% TOP1630 or Placebo Dose Comfort Assessment Evening 0.01% TOP1630 or Placebo Dose Visual Acuity, Slit Lamp Biomicroscopy, IOP, and Comfort Assessment Subject leaves clinic at completion of Visit.
Visit 2a (Day 2: 24 +/- 3 hrs after first dose): Physician Assessment	Medical/Medication Update, AE Query, Vital Signs Visual Acuity, Slit Lamp Biomicroscopy, IOP
Visit 3a (Day 3) TOP1630 0.1% or Placebo QD	Medical/Medication Update, AE Query, Vital Signs Visual Acuity, Slit Lamp Biomicroscopy, IOP 0.1 % TOP1630 or Placebo Dose (QD) Comfort Assessment Visual Acuity, Slit Lamp Biomicroscopy, IOP Subject leaves clinic at end of visit
Visit 4a (Day 4: 24 +/- 3 hrs after Day 3 dose): Physician Assessment	Medical/Medication Update, AE Query, Vital Signs Visual Acuity, Slit Lamp Biomicroscopy, IOP
Visit 5a (Day 5):	Medical/Medication Update, AE Query, Vital Signs Visual Acuity, Slit Lamp Biomicroscopy, IOP, and

TOP1630 0.1% or Placebo TID	Comfort Assessment Morning 0.1% TOP1630 or Placebo Dose Slit Lamp Biomicroscopy, Comfort Assessment Afternoon 0.1 % TOP1630 or Placebo Dose Comfort Assessment Evening 0.1% TOP1630 or Placebo Dose Visual Acuity, Slit Lamp Biomicroscopy, IOP, and Comfort Assessment Subject leaves clinic at completion of Visit
Visit 6a (Day 6: 24 +/- 3 hrs after Day 5 dose): Physician Assessment	Medical/Medication Update, AE Query, Vital Signs Visual Acuity, Slit Lamp Biomicroscopy, IOP
Visit 7a (Day 8): Multi-Dose Phase Start	Medical/Medication Update, AE Query, Vital Signs Visual Acuity, Slit Lamp Biomicroscopy, IOP 0.1 % TOP1630 or Placebo TID (at home) Comfort Assessment (at home) Study Drug for at-home dosing and Comfort Questionnaire dispensed
Subject will dose 0.1% TOP1630 or Placebo TID at home on Days 8-11. No site visits.	
Visit 8a (Day 12: 24 +/- 3 hrs after first dose on Day 11): Study Exit	Collection of Study Drug/Comfort Questionnaire Medical/Medication Update, AE Query, Vital Signs Visual Acuity, Slit Lamp Biomicroscopy, IOP Urine Pregnancy Testing (as needed) Study Exit

Analysis of the Comfort Assessment will be conducted in a blinded manner to ensure study stopping criteria have not been met and to confirm the dose for the 4 week Safety and Efficacy Assessment. If study stopping criteria have been met, unmasking may be needed to fully assess the data prior to dose selection. A separate study plan will be created to outline the process for evaluation of stopping criteria and dose selection for the Safety and Efficacy Assessment.

For the Safety and Efficacy Assessment, 60 subjects at least 18 years of age with a subject-reported history of dry eye in both eyes and meeting all other study eligibility criteria will be randomized to receive treatment with TOP1630 Ophthalmic Solution (dose determined by outcome of Comfort Assessment) or placebo in a 1:1 ratio (approximately 30 subjects in each treatment group). This study will consist of two periods: a 7-day run-in period and a 28-day treatment period. A study flow chart appears below:

Visit 1b (Day -7 ± 1): Screening	Informed Consent Demographics, Medical/Medication & Ocular History Vital Signs Urine Pregnancy Testing (as needed) Symptom Questionnaires, Visual Acuity Pre-CAE® Eye Evaluations CAE® Exposure Post-CAE® Eye Evaluations
---	--

Subjects who terminate early during the treatment period will be asked to complete safety assessments prior to commencement of any alternative dry eye treatment (if possible) according to PI judgment. Subjects who are terminated early from the study will not be replaced.

## 5 STUDY POPULATION

### 5.1 Number of Subjects (approximate)

For the Comfort Assessment, it is estimated that, assuming a 60% screen failure rate, approximately 20 subjects will be screened to enroll 8 randomized subjects in a 3:1 ratio (6 in the TOP1630 arm and 2 in the placebo arm).

For the Safety and Efficacy Assessment, it is estimated that, assuming a 60% screen failure rate, approximately 150 subjects will be screened to enroll approximately 60

randomized subjects. Subjects will be randomized in a 1:1 ratio (30 subjects in the TOP1630 arm and 30 in the placebo arm).

## 5.2 Study population characteristics

### Inclusion Criteria

Subjects must meet all of the following requirements to be eligible for enrollment into the study:

For the Comfort Assessment:

1. Be at least 18 years of age;
2. Provide written informed consent;
3. Have a patient reported history of dry eye for at least 6 months prior to Visit 1a;
4. Have a history of use or desire to use eye drops for dry eye symptoms for at least 6 months prior to Visit 1a;

For the Safety and Efficacy Assessment:

All of the above criteria (at Visit 1b), and:

5. Report a score of  $\geq 2$  in at least one symptom of the Ora Calibra® Ocular Discomfort & 4-Symptom Questionnaire at Visits 1b and 2b;
6. Report an OSDI® score  $\geq 18$  at Visits 1b and 2b;
7. Have a conjunctival redness score of  $\geq 1$  according to the Ora Calibra® scale in at least one eye at Visits 1b and 2b;
8. Have a tear film break-up time (TFBUT)  $>1$  and  $< 7$  seconds in at least one eye at Visit 1b and 2b;
9. Have a Schirmer's Test score of  $\leq 10$  mm and  $\geq 1$  mm in at least one eye at Visits 1b and 2b;
10. Have a corneal fluorescein staining score of  $\geq 2$  according to the Ora Calibra® scale in at least one region (e.g. inferior, superior, or central) in at least one eye at Visits 1b and 2b;
11. Have a total lissamine green conjunctival score of  $\geq 2$ , based on the sum of the temporal and nasal regions of the conjunctiva according to the Ora Calibra® scale in at least one eye at Visits 1b and 2b;
12. Demonstrate a response to the CAE® at Visits 1b and 2b as defined by:
  - a. Having at least a  $\geq 1$  point increase in fluorescein staining in the inferior region in at least one eye following CAE® exposure on the Ora Calibra® scale; and
  - b. Reporting an Ocular Discomfort score  $\geq 3$  at 2 or more consecutive time points in at least one eye during CAE® exposure on the Ora Calibra® scale (if a subject has an Ocular Discomfort rating of 3 at time = 0 for an eye, s/he must report an Ocular Discomfort rating of 4 for two consecutive measurements for that eye).

13. Have at least one eye (the same eye) satisfy all criteria for 7, 8, 9, 10, 11, and 12 above;
14. At Visit 2b, subjects must have at least 5 days' worth of diary symptom data and deemed by the PI to be 80% compliant with vehicle eye drops.

### **Exclusion Criteria**

Subjects may not participate in the study (Comfort Assessment as well as the Safety and Efficacy Assessment) if any of the following criteria are met:

1. Unable or unwilling to follow instructions, including participation in all study assessments and visits;
2. Have any clinically significant slit lamp findings at Visit 1 (1a or 1b) that may include active blepharitis, meibomian gland dysfunction (MGD), lid margin inflammation or active ocular allergies that require therapeutic treatment, and/or in the opinion of the investigator may interfere with study parameters;
3. Be diagnosed with an ongoing ocular infection (bacterial, viral, or fungal), or active ocular inflammation at Visit 1 (1a or 1b);
4. Have any significant ocular lesion that could interfere with assessment of safety or efficacy or prevent study conduct in the opinion of the PI;
5. Have worn contact lenses within 14 days of Visit 1 (1a or 1b) or anticipate using contact lenses during the study;
6. Have used any eye drops within 2 hours of Visit 1 (1a or 1b);
7. Have previously had laser-assisted *in situ* keratomileusis (LASIK) surgery within the last 12 months or any other ocular surgeries within the last 6 months;
8. Have used Restasis® or Xiidra™ within 90 days of Visit 1 (1a or 1b);
9. Have used topical ocular steroids within 30 days of Visit 1 (1a or 1b);
10. Have any planned ocular and/or lid surgeries over the study period;
11. Have temporary punctal plugs at Visit 1 that have not been stable within 45 days of Visit 1 (1a or 1b) or anticipate having temporary punctal plugs inserted during the study;
12. Have had punctal occlusion (not including punctal plugs) within 6 months of Visit 1(1a or 1b);
13. Be currently taking any topical ophthalmic prescription (including medications for glaucoma) or over-the-counter (OTC) solutions, artificial tears, gels or scrubs, and cannot discontinue these medications for the duration of the trial (excluding medications allowed for the conduct of the study) or have used any of these medications in the previous 24 hours prior to visit 1 (1a or 1b);
14. Have corrected visual acuity greater than or equal to logMAR+0.7 as assessed by Early Treatment of Diabetic Retinopathy Study (ETDRS) scale in both eyes at Visit 1 (1a or 1b);
15. Have an uncontrolled systemic disease;
16. Be a woman who is pregnant, nursing or planning a pregnancy;
17. Be unwilling to submit a urine pregnancy test at Visit 1 (1a or 1b) and Visit 8a or 4b (or early termination visit) if of childbearing potential. Non-

childbearing potential is defined as a woman who is permanently sterilized (e.g. has had a hysterectomy or tubal ligation), or is post-menopausal (without menses for 12 consecutive months);

18. Be a woman of childbearing potential who is not using an acceptable means of birth control; acceptable methods of contraception include: hormonal – oral, implantable, injectable, or transdermal contraceptives; mechanical – spermicide in conjunction with a barrier such as a diaphragm or condom; IUD; or surgical sterilization of partner. For non-sexually active females, abstinence may be regarded as an adequate method of birth control; however, if the subject becomes sexually active during the study, she must agree to use adequate birth control as defined above for the remainder of the study;
19. Have a known allergy and/or sensitivity to the test article or its components;
20. Have a condition or be in a situation which the investigator feels may put the subject at significant risk, may confound the study results, or may interfere significantly with the subject's participation in the study;
21. Be currently enrolled in an investigational drug or device study or have used an investigational drug or device within 30 days of Visit 1 (1a or 1b). Subjects that were enrolled in the Comfort Assessment will be excluded from participating in the Safety and Efficacy Assessment;
22. Be currently using any medication known to cause ocular drying that is not used on a stable dosing regimen for at least 30 days prior to Visit 1 (1a or 1b); antihistamines are not allowed at any time during the study.

### **5.3 Withdrawal Criteria and Study Stopping Criteria**

Subjects may withdraw consent from study participation at any time.

If at any time during the study the investigator determines that a subject's safety is or has been compromised, the subject may be withdrawn from the study.

Subjects may be discontinued prior to their completion of the study due to the following safety stopping criteria being met for any subject:

- Persistent loss of 3 or more lines of visual acuity not explained by the condition under investigation and confirmed upon repeat testing
- Development of persistent corneal opacities or severe keratitis
- Persistent ocular irritation or redness not explained by condition
- IOP increase of 12 or more confirmed upon repeat testing
- Sight threatening adverse events such as corneal melting or corneal ulceration;
- Any other possibly related adverse events

Other reasons for discontinuation:

- Protocol violations

- Administrative reasons (e.g., inability to continue, lost to follow up)
- Subject choice (e.g. withdrawal of consent)
- Non compliance
- Any valid medical reason at discretion of investigator (see section 8.6.2)
- Other

Notification of a subject discontinuation and the reason for discontinuation will be made to Ora and/or study Sponsor and will be clearly documented in the eCRF.

Discontinued subjects will not be replaced.

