**8.2.2 Escape Medications**

No escape medications are allowed for this study.

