### **Early Termination/Discontinuation**

If a subject is discontinued from the study prior to Visit 8a or 4b, then all safety evaluations that were to be performed at the Visit should be performed on the day of discontinuation (early termination) or at the discretion of the investigator.

Adverse Events (both elicited and observed) and SAEs will be monitored throughout the study. The investigator will promptly review all adverse events (both elicited and observed) for accuracy and completeness. All adverse events will be documented on the appropriate source document and case report form.

If a female reports a pregnancy or has a positive pregnancy test during the study the investigator will notify Ora immediately. The investigator shall request from the subject and/or the subject’s physician copies of all related medical reports during the pregnancy and shall document the outcome of the pregnancy. The investigator will retain these reports together with the subject’s source documents and will provide a copy of all documentation to Ora.

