## **8.5 Compliance with Protocol**

Subjects will be instructed on proper use of the subject daily diary and proper instillation and storage of study drug at the end of Visit 1a and 7a (in the Comfort Assessment) and Visits 1b, 2b, and 3b (in the Safety and Efficacy Assessment) and given written instructions. In the Comfort Assessment, used and unused study drug bottles will be collected at Visit 8a. In the Safety and Efficacy Assessment, the subject daily diaries and used and unused study drug bottles will be collected at each visit from Visit 2b up to and including Visit 4b to assess dosing and symptom assessment compliance. Dosing compliance will be based on the used and unused bottle count. If the subject is less than 80% or more than 114% compliant with dosing based on the expected number of used bottles, then the subject will be deemed non-compliant and a deviation should be recorded.

In the Safety and Efficacy study, subjects must have at least 5 days' worth of diary symptom data and deemed by the Investigator to be at least 80% compliant with dosing during the placebo run-in to be able to continue in the study. In the subject daily diary, if more than 20% of applicable Dose Taken boxes are checked “no”, left blank, or missing for a diary period, a subject will be deemed non-compliant and a diary deviation will be recorded. If more than 20% of the total diary symptom assessments for that dosing period are missed, these subjects will be deemed non-compliant and a diary symptom assessment deviation will be recorded. These guidelines will be used by the Investigator for determining the subject's necessary compliance for the study and for recording deviations from this compliance.

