9.5 Adjustments for Multiplicity

There will be no adjustments for multiple endpoints or multiple treatment comparisons for this early phase, exploratory study.

10. Disposition of Subjects

Subject disposition will be presented in terms of the numbers and percentages of subjects who were randomized, completed the study, and discontinued from the study. Subjects who are not discontinued from the study will be considered study completers. Disposition will be summarized by treatment group and for all subjects.

The number and percentage of subjects discontinued from the study and the reasons for study discontinuation will be summarized by treatment group for all randomized subjects. The reasons for study discontinuation that will be summarized include: AEs, protocol violations, administrative reasons, sponsor termination of study, subject choice, and other. A subject listing will be provided that includes the date of and reason for premature study discontinuation.

The number and percentage of subjects with protocol deviations will be summarized by treatment group for all randomized subjects. A subject listing will be provided that includes the date of the deviation, the deviation description and the classification of whether the deviation was judged to be major or minor.

In addition, subject listings will be provided that include informed consent date, inclusion and exclusion criteria violations, and exclusions from the PP population.

11. Demographic and Baseline Variables

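### Section 5.3 permits removing randomised subjects from the study for violations or non-compliance, where Section 8.5 asks only for a recorded deviation; the efficacy data lost may be related to outcome

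*Protocol*

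**What the plan says.** **Grounds for leaving the study.** Protocol Section 5.3 opens its safety list with "Subjects may be discontinued prior to their completion of the study". A second list, "Other reasons for discontinuation", adds "Protocol violations" and "Non compliance" beside administrative reasons, subject choice, medical reasons and a residual category. Neither entry is tied to a study period. Those who leave are not replaced.

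**Compliance.** Protocol Section 8.5 sets limits: bottle use below 80% or above 114%, or more than 20% of diary dose boxes or symptom entries missing. Being allowed to continue depends on compliance only for the placebo run-in. After that, the stated consequence is a deviation. The closing sentence, "These guidelines will be used by the Investigator for determining the subject's necessary compliance for the study", goes on to give the recording of deviations as a second use of the limits.

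**Exit data.** Under Early Termination/Discontinuation in Protocol Section 8.3.1, "all safety evaluations that were to be performed at the Visit should be performed on the day of discontinuation", or at the investigator's discretion. Efficacy assessments are not mentioned there, and no visits after discontinuation are planned.

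**Analysis.** Efficacy uses observed data in the mITT, which requires one post-baseline efficacy assessment (SAP 8.1, 9.2). LOCF and multiple imputation cover only Ora Calibra corneal staining and ocular discomfort (SAP 16). The PP set removes significant deviations and non-completers (SAP 8.2).

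**Reporting.** SAP Section 10: "The reasons for study discontinuation that will be summarized include: AEs, protocol violations, administrative reasons, sponsor termination of study, subject choice, and other". Non-compliance has no line of its own.

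**The concern.** Sections 5.3 and 8.5 give different consequences for the same randomised subject, and the choice is left to the investigator. Under 8.5 the subject stays and a deviation is logged. Under 5.3 the subject may leave, and the remaining efficacy data are then never collected.

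This matters if the choice is related to outcome, and it plausibly is. Protocol Section 8.2.2 says "No escape medications are allowed for this study", and exclusion 13, carried through the study by Section 8.2.1, bars other eye drops. A subject without relief who turns to such drops has violated the protocol. A subject who finds the study drops uncomfortable may skip doses. Both routes are inferences about behaviour; the documents do not report them.

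Removal gains nothing analytically, because the PP set already handles significant deviations. What is at stake is the randomised comparison for every endpoint without imputation, in a study meant to supply efficacy data for planning later trials.

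**Working it through.** **The plan's own figure.** The only probability given is 79% for detecting an adverse event with a 5% rate (Protocol 10.3). It is reproduced by 1 − 0.95^30 = 0.785, so it is a per-arm figure. It does not bear on retention. The documents give no drop-out, violation or non-compliance rate, so every rate below is an assumption.

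**Step 1: when removal can happen.** Bottles and diaries are reviewed at Visits 2b, 3b and 4b. Visit 2b precedes randomisation and Visit 4b is study exit, so scheduled compliance review can cause loss only around Visit 3b. The Visit 3b procedure list puts that review before the efficacy assessments.
- Removed at or before that check: no post-baseline clinic efficacy data. Mid-trial diary scores might still qualify the subject for the mITT, but the definition does not say. The protocol synopsis words the mITT more widely (any assessment after Visit 2), but membership on that basis would not supply the missing efficacy values.
- Removed after Visit 3b: stays in the mITT with Visit 3b data, absent at Visit 4b.

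**Step 2: effect on the sets at Visit 4b.** With 60 randomised, a share v with a significant violation and a fraction q of those discontinued, observed mITT = 60 × (1 − v × q) and PP = 60 × (1 − v).

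| v | q | mITT observed at 4b | PP |
|---|---|---|---|
| 10% | 0 | 60 | 54 |
| 10% | 0.5 | 57 | 54 |
| 10% | 1 | 54 | 54 |
| 20% | 0 | 60 | 48 |
| 20% | 0.5 | 54 | 48 |
| 20% | 1 | 48 | 48 |

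The sets coincide only if every significant violator is removed.

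**Step 3: shift in the observed difference, simple form.** Let d be the share removed in an arm and g the number of SDs by which removed subjects would have done worse than those who stay. The observed arm mean then looks better by d × g, and with the same g in both arms the difference shifts by (d placebo − d active) × g.
- 20% and 10%: 0.10 × 0.5 = 0.05 SD; 0.10 × 1 = 0.10 SD.
- 20% and 5%: 0.15 × 0.5 = 0.075 SD; 0.15 × 1 = 0.15 SD.
- Equal shares and equal g: 0.

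**Step 4: the same shift with g set by a correlation.** Suppose removal takes the upper tail of a latent normal variable that correlates r with a worse outcome. The arm mean then shifts by r × φ(z) / (1 − d), where z cuts off the upper share d.
- d = 15%: z = 1.036, φ = 0.2332, and 0.2332 / 0.85 = 0.274.
- d = 5%: z = 1.645, φ = 0.1031, and 0.1031 / 0.95 = 0.109.
- Difference: 0.274 − 0.109 = about 0.166, multiplied by r.

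| r | Shift (SD) | True 0.50 SD, placebo loses 15%, active 5% | True 0.50 SD, arms reversed |
|---|---|---|---|
| 0.3 | 0.05 | 0.45 | 0.55 |
| 0.5 | 0.08 | 0.42 | 0.58 |
| 1.0 | 0.17 | 0.33 | 0.67 |

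In arms of 30, the 15%/5% split is about 4.5 against 1.5 subjects. The 0.50 SD effect is also assumed, but the shift does not depend on it. Correlation 1.0 means that exactly the worst outcomes are removed; it is an upper bound and not a realistic case.

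**The case against.** The strongest reply is that Section 5.3 is a permissive list that documents why people leave and does not instruct anyone to remove them. The rest of the plan expects non-compliers to stay. SAP 13.1 tabulates compliance below 80% and above 114% whatever the completion status. The PP definition sets freedom from significant deviations and completion as separate conditions, which is natural only if some violators complete. The two key endpoints have LOCF and multiple imputation. All of this stands, and it limits how many subjects are likely to be lost. It does not remove the discretion, and imputation does not recover uncollected data or cover the other endpoints.

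Three stronger readings are tempting.
- **A reader might infer that Section 8.5 calls for removal once the limits are crossed.** It does not. After randomisation it names only a deviation.
- **A reader might infer that subjects who dislike the drops lose their Week-4 safety examinations.** The early-termination text brings these forward to the exit day or leaves them to discretion. Drop comfort is collected only at Visits 2b and 3b, so no Week-4 comfort data exist to lose. Persistent irritation is also a listed safety reason in its own right. What is lost is the planned four-week timing, which matters most for intraocular pressure, fundoscopy and corneal sensitivity, whose only post-baseline measurement is scheduled at Visit 4b.
- **A reader might infer that loss of power is the harm.** The study is expressly not powered for efficacy, so that argument is weak.

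The missing non-compliance category in SAP Section 10 is minor: the list is not worded as exhaustive, and a listing gives each subject's reason.

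**Conclusion.** The concern holds in a limited form. Sections 5.3 and 8.5 disagree on a randomised subject who violates the protocol or does not comply, and the Section 5.3 route ends efficacy follow-up. If such exits are related to outcome and unequal between arms, the observed-data mITT comparison is biased. On the assumed 15%/5% split the shift is about 0.05, 0.08 or 0.17 SD at correlations 0.3, 0.5 and 1.0. It is towards no effect if placebo loses more of its worst cases and away from it if active does. It is zero if the losses are equal and equally severe. Neither the split nor the correlation is in the documents, so the direction cannot be stated.

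A reader might go further and conclude that the mITT result will become a per-protocol result. That requires all, or nearly all, significant violators to be removed, and the documents point the other way.

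**What to change.** Reconcile Protocol Section 5.3 with Section 8.5 so that, after randomisation:
- protocol violations and non-compliance are recorded as deviations and are not in themselves a reason to end study follow-up, including when entered under an administrative or residual category;
- subjects who still consent are kept on the scheduled Visit 3b and 4b efficacy and safety assessments;
- they are analysed as randomised in the mITT and excluded only from the PP set, if the deviation is significant.

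The change concerns data collection only. Decisions on dosing, withdrawal for safety and withdrawal of consent stay as they are.

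The cost is a short amendment and site training, with no visits or procedures beyond those already scheduled. The mITT estimate may be slightly diluted by non-compliers, and the PP analysis is already there to show that.
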